10.2. Record Maintenance and Retention

The investigator-sponsor will maintain records in accordance with Good Clinical Practice guidelines; to include:

- FDA correspondence related to the IND and clinical protocol, including copies of submitted Safety Reports and Annual Reports
- IRB correspondence (including approval notifications) related to the clinical protocol; including copies of adverse event reports and annual or interim reports
- Current and past versions of the IRB-approved clinical protocol and corresponding IRB-approved consent form(s) and, if applicable, subject recruitment advertisements
- Signed FDA Form 1572 Statements of Investigator (i.e., for the investigator-sponsor and all identified sub-investigators)
- Financial disclosure information (investigator-sponsor and clinical protocol sub-investigators)
- Curriculum vitae (investigator-sponsor and clinical protocol sub-investigators)
- Certificates of required training (e.g., human subject protections, Good Clinical Practice, etc.) for investigator-sponsor and listed sub-investigators
- Listing of printed names/signatures of investigator-sponsor and listed sub-investigators

- Normal value(s)/range(s) for medical/laboratory/technical procedures or tests included in the clinical protocol
- Laboratory certification information
- Instructions for on-site preparation and handling of the investigational drug(s), study treatment(s), and other study-related materials (i.e., if not addressed in the clinical protocol)
- Decoding procedures for blinded trials (*as described in the section “breaking the Blind”*)
- Master randomization list
- Signed informed consent forms
- Completed Case Report Forms; signed and dated by investigator-sponsor
- Source Documents or certified copies of Source Documents
- Monitoring visit reports
- Copies of investigator-sponsor correspondence to sub-investigators, including notifications of safety information
- Subject screening and enrollment logs
- Subject identification code list
- Investigational drug accountability records, including documentation of drug disposal.
- Final clinical study report

Research data and documents will be stored in locked/secure areas accessible to investigators and research staff of the study. Research data and documents may also be stored on protected network drives, accessible only to researchers. The investigators and research staff involved with the study will make every effort to maintain the subjects' confidentiality. Much of the research data will be coded and kept without identifiers' to ensure subject confidentiality. To achieve this, all subjects will be assigned a sequential subject number, which will be used to mark Case Report Forms, subject folders or binders, and testing forms. Identifiable information, such as the linkage codes used to identify subjects with their subject IDs, will be kept in secured areas accessible only to the investigator and research staff involved with the study. Subject names or directly identifiable information will not appear on any reports, publications, or other disclosures of study outcomes. Should the subjects decide to withdraw from study participation, information previously collected from the subjects will continue to be maintained in the same manner as other research data collected for this study.

The investigator-sponsor will retain the specified records and reports for up to 2 years after the marketing application is approved for the investigational drug; or, if a marketing application is not submitted or approved for the investigational drug, until 2 years after investigations under the IND have been discontinued and the FDA so notified.

10.3 Data Sharing

As part of the conditions of the grant from SMRI which funds this study, we will submit de-identified subject data to the National Institute of Mental Health Data Archive (NDA), specifically the National Database for Clinical Trials Related to Mental Illness (NDCT). The types of data we will submit include the following: demographic data and data from diagnostic and symptom assessments.

11. Ethics

11.1 Institutional Review Board (IRB) Approval

The investigator-sponsor will obtain, from the University of Maryland and UCLA Institutional Review Boards (IRB's), prospective approval of the clinical protocol and corresponding informed consent form(s); modifications to the clinical protocol and corresponding informed consent forms, and advertisements (i.e., directed at potential research subjects) for study recruitment.

The only circumstance in which a deviation from the current IRB-approved clinical protocol/consent form(s) may be initiated in the absence of prospective IRB approval is to eliminate an apparent immediate hazard to the research subject(s). In such circumstances, the investigator-sponsor will promptly notify the IRB of the deviation.

The IRB's operate in compliance with FDA regulations at [21 CFR Parts 50](#) and [21 CFR 56](#), and in conformance with applicable International Conference on Harmonization (ICH) Guidelines on Good Clinical Practice (CGP).

In the event that one of the IRB's requires, as a condition of approval, substantial changes to a clinical protocol submitted under an FDA-accepted IND application, or in the event of an investigator-sponsor's decision to modify the previously accepted clinical protocol:

- **for a Phase 1 clinical study:** The investigator-sponsor will submit (i.e., in advance of implementing the change) a Protocol Amendment to the IND describing any change to the Phase 1 clinical protocol that significantly affects the safety of the subjects. For changes that do not affect critical safety assessments, the revisions to the clinical protocol will be addressed in the Annual Report to the IND.
- **for Phase 2 and 3 clinical studies:** The investigator-sponsor will submit (i.e., in advance of implementing the change) a Protocol Amendment to the IND describing any change to a Phase 2 or Phase 3 protocol that significantly affects the safety of subjects, the scope of the investigation, or the scientific quality of the study. Examples of Phase 2 and 3 clinical protocol changes requiring the submission of a Protocol Amendment include:

- Any increase in drug dosage or duration of exposure of individual subjects to the investigational drug beyond that described in the current protocol, or any significant increase in the number of subjects under study.
- Any significant change in the design of the protocol (such as the addition or deletion of a control group).
- The addition of a new test or procedure that is intended to improve monitoring for, or reduce the risk of, a side effect or adverse event; or the dropping of a test intended to monitor the safety of the investigational drug.

11.2 Ethical and Scientific conduct of the Clinical Study

The clinical study will be conducted in accordance with the current IRB-approved clinical protocol; ICH Guidelines on GCP; and relevant policies, requirements, and regulations of the Universities and applicable federal agencies.

Subject Informed Consent

The investigator-sponsor will make certain that an appropriate informed consent process is in place to ensure that potential research subjects, or their authorized representatives, are fully informed about the nature and objectives of the clinical study, the potential risks and benefits of study participation, and their rights as research subjects. The investigator-sponsor, or a sub-investigator(s) designated by the investigator-sponsor, will obtain the written, signed informed consent of each subject, or the subject's authorized representative, prior to performing any study-specific procedures on the subject. The date and time that the subject or the subject's authorized representative, signs the informed consent form and a narrative of the issues discussed during the informed consent process will be documented in the subject's case history. The investigator-sponsor will retain the original copy of the signed informed consent form, and a copy will be provided to the subject, or to the subject's authorized representative.

The investigator-sponsor will make certain that appropriate processes and procedures are in place to ensure that ongoing questions and concerns of enrolled subjects are adequately addressed and that the subjects are informed of any new information that may affect their decision to continue participation in the clinical study. In the event of substantial changes to the clinical study or the risk-to-benefit ratio of study participation, the investigator-sponsor will obtain the informed consent of enrolled subjects for continued participation in the clinical study

11.3 Investigator-Sponsor Discontinuation Criteria

Criteria and procedures for terminating the participation of an individual study subject

A research subject will be terminated from study participation in the event that:

1. Subject fails to follow-up with study procedures and study visits despite reasonable efforts on the part of the research staff to contact him/her will be discontinued from the study.
2. Subject experiences a serious adverse event that is unanticipated and thought to be possibly related to study drug will be discontinued from the study.
3. An unanticipated and serious adverse event emerges and is considered related or possibly related to study drug, the study may be stopped and all currently participating subjects contacted to stop taking the study drugs and complete any final study procedures (safety associated laboratory test, etc). The DSMB, IRB and FDA will be notified on such actions.
4. A female subject becomes pregnant during study participation.

Note: Missing multiple doses of study treatment does not qualify as a reason for termination. Participants who miss multiple doses will be encouraged to resume study medication at the standard BID schedule. However, if it is determined that a participant's study drug treatment has been interrupted for greater than 7 consecutive days, that individual may be considered for removal from the study by the investigator-sponsor.

Termination procedures:

- Perform a final on-site or telephone assessment of adverse event occurrence.
- Request the return of any remaining study drug doses. If necessary, send a pre-paid envelope to the participant and include a request that the participant return the study drug as soon as possible.
- Complete study drug accountability record to account for any returned doses and the subsequent disposal of such doses in accordance with guidelines of the Investigational Drug Service

Subjects withdrawn due to a serious unexpected adverse event will only be replaced once full assessment of the event has taken place, in order to ensure the safety of additional subjects. Replacements will occur in this study only up to the limits allowed by availability of subjects' budget considerations.

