3.3 Recruitment Targets and Timelines

3.4 Schedule of Events

Approximate Visit Intervals	V1	V2	V3	V4	V5	V6	V7	V8
				2 wks	4 wks	6 wks	8 wks	10 wks
Informed Consent, Urine Drug Test, Pregnancy test, Psychiatric		X						
Diagnosis and History, Medical History								
Labs, EKG ¹		X						X
PANSS, CGI, PSS ²	X	X	X	X		X		X
MCCB		X				X		X
BP, Pulse, Temperature Weight, Height ³	X	X	X	X	X	X	X	X
Sensoril or Placebo		X	X	X	X	X	X	X
Treatment Emergent Adverse Events or Serious Adverse Events			X	X	X	X	X	X

Visit Comments, Pill Counts ⁴	X	X	X	X	X	X	X	X
--	---	---	---	---	---	---	---	---

Visit 1 can be split up (if needed) into 2 visits for screening and spread over 1 to 4 weeks. Visit 2 is the randomization visit. Following randomization, visit intervals for V3 through V8 can range from \pm 4 days of the expected between interval visits; exceptions on a case by case basis by the study team.

Visits 1 and 8 will last roughly 2 hours. Visits 2, 3, 4, 5, 6, and 7 will last roughly 1 hour.

At Visit 1 – Urine drug test for illicit substances will occur as will a serum pregnancy test for women in the reproductive age group.

¹Labs: CBC + Diff, Chemistry 14? (including liver and renal functions, electrolytes, blood sugar, and lipid profile), urine analysis, and hs CRP and serum for cytokine panels

¹EKG: standard EKG

² The Positive and Negative Syndrome Scale (PANSS), Clinical Global Impression Scale (CGI), Perceived Stress Scale (PSS),

³ Height at screening only, waist circumference and BMI at screening and visit 8 or end of study.

⁴ Pill Counts – will start at visit 3, i.e., post randomization

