5.3 Treatment Adherence/Study Compliance

Once the dispensing of the medication begins, adherence will be recorded by the study coordinator on log sheets in the research binder during each visit. Adherence will be based on discussions with participant and returned capsule counts. Participants who withdraw consent or whose clinical status worsens to prevent continuation in the study will be withdrawn and stabilized under standard clinical care conditions. There is no open continuation phase in this study. Participants will be counseled about this issue prior to initiating the study and advised

that Sensoril® may be obtained over the counter or via the internet through a general nutritional supplement outlet.

Participants who are found to be non-compliant with daily dosing of Sensoril®/placebo for a period of 7 consecutive days during the 12 week study period, or are otherwise found to be significantly non-compliant with study procedures and/or investigator instructions may be withdrawn from study participation.

If there are more dropouts than anticipated and other considerations (e.g. budget, etc.) permit more participants to be recruited, we may modify our protocol and consent and request the IRB to recruit more participants until we have 66 participants with evaluable primary efficacy data.

6. Drug Supplies

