7.3. Efficacy and Safety Assessments

As noted in the Schedule of Events table, psychopathology (PANSS, CGI) and stress (PSS) scales will be assessed at every visit and will form the measurements required for affirming the primary efficacy outcomes, and will inform future studies about the size of the WSE treatment effects. These scales will also assist in monitoring psychopathology and stress as safety concerns.

Psychotropic Medications

These medications are listed in the database by name, daily dosage, start and stop dates. This will permit coding of increases (or decreases) in doses of existing medications, stopping of existing medications (e.g. stopping an existing antipsychotic and starting a new one), etc. Further discussion of the data analysis is provided in section 9.1.c – Psychotropic Medication End Points

Safety Assessments

During the screening process, a review of the medical history, recording of vital signs, laboratory and EKG assessments will provide safety data to the PI and research staff, and help them assess suitability of the subject for the study.

Side-effects will be monitored at each visit, by asking an open ended question and following up with the MPRC Side Effect Checklist. Based on the nature of the side effects, these may be attended to by either reducing the dosage, discontinuing study capsules, with follow-up

laboratory and/or physical examinations, or consultations, until resolution occurs. Recording of vital signs, the use of psychopathology and stress rating scales will further assist in evaluating safety of participating participants.

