7.12. Withdrawal of Participants Due to Adverse Events

If unanticipated and serious adverse events emerge and are considered related or possibly related to study drug, the study may be stopped and all currently participating participants will be contacted to stop taking the study drugs and complete any final study procedures (safety associated laboratory test, etc). The respective IRBs and FDA will be notified of such actions by the investigators at each site, and by the IND holder at Pittsburgh to the FDA.

Similarly, if the holder of the CTD, Natreon, Inc informs the IND holder or the PI/Co-I of unanticipated adverse events that have emerged and could place currently enrolled participants at greater risk for physical and psychological harm than anticipated then actions for stopping the study and follow-up as described above will be initiated by the PI and research staff in conjunction with the IND holder and other responsible entities (e.g. FDA).

8. Statistical Methods/Data Analysis

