8.1 Primary Endpoint(s)

For *Specific Aim 1*, an intention-to-treat strategy will be used for analysis and participants will be analyzed as part of the group to which they were randomized. A linear mixed model will be used to examine changes in measures of psychopathology (PANSS Total, Positive and Negative Symptoms and General Psychopathology Subscales) and psychosocial stress (PSS). For the primary endpoint (PANSS Total Score), a model that includes visit, treatment, visit * treatment interaction as fixed effects with baseline PANSS total score as a covariate will be used. Model-estimated marginal means for scheduled

visits will be computed per treatment group to examine time to response. Linear mixed models use all available data, account for non-independence of repeated measures and provide unbiased estimates if missing data are present.

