8.3. Definition(s): Analysis population(s)

Any participant who provides informed consent and completes screening procedures, and receives randomized study medication, and also comes in for at least one additional study visit will form the safety population for data analyses.

Any participant who was randomized and provided baseline plus at least one other visit where the PANSS and PSS scales assessments were reassessed will form the intent to treat population for efficacy analyses for the primary outcomes.

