8.6 Sample size calculation

In a previous 12-week, double-blind, placebo-controlled study that examined the efficacy of WSE (Sensoril®) for the treatment of symptom exacerbations in participants with schizophrenia (Chengappa et al, in press: J Clin Psychiatry), participants randomized to Sensoril® had a significantly greater reduction in PANSSS total score (effect size=0.83); the primary outcome measure in the current study. If we assume the same effect size, then a sample of 66 (33 in each group) will have a power of 0.95 to detect an effect size of 0.83 with a 1-tailed alpha set at 0.05 and power of 0.90 with a 2-tailed test of significance (see Table). The proposed sample size will allow for us to continue to have sufficient power (i.e., 0.80), even if a significant number of randomized participants fail to provide data for the proposed analyses.

Power	Sample (1-tailed)	Sample (2-tailed)
0.80	$19 + 19 = 38$	$24 + 24 = 48$
0.85	$22 + 22 = 44$	$28 + 28 = 56$
0.90	$26 + 26 = 52$	$32 + 32 = 64$

0.95	33 + 33 = 66	39 + 39 = 78
------	--------------	--------------

9. Quality Control and Quality Assurance

Independent monitoring of the clinical study for protocol and GCP compliance will be conducted periodically by qualified staff of the UCLA and University of Maryland Human Subject Protection Offices.

The investigator-sponsor and the University of Maryland and UCLA will permit direct access of the study monitors and appropriate regulatory authorities to the study data and to the corresponding source data and documents to verify the accuracy of this data.

Details of the Data and Safety Monitoring Committee are noted in section **7.4**.

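### No PANSS is specified at early withdrawal, so worsening after the last rating can go unrecorded and the mixed model is not assured of being unbiased

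*Combined protocol and SAP*

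**What the plan says.** Section 11.3 is the only place that sets out what is done when an individual leaves. Its steps are "Perform a final on-site or telephone assessment of adverse event occurrence", recovery of unused capsules, and completion of the accountability record. No symptom rating is among them.

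Worsening as a reason to leave is in section 5.3, not in the numbered list of 11.3. Under 5.3, participants "whose clinical status worsens to prevent continuation in the study will be withdrawn and stabilized under standard clinical care conditions". No final rating is mentioned there either.

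The schedule in section 3.4 has no early-termination column. Its one end-of-study alternative is in a footnote: "waist circumference and BMI at screening and visit 8 or end of study". After randomisation, the PANSS/CGI/PSS row is marked at V3, V4, V6 and V8. Section 7.3 says otherwise: "psychopathology (PANSS, CGI) and stress (PSS) scales will be assessed at every visit". Section 3.1 also has psychopathology rated at each visit.

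On analysis, section 8.1 says: "Linear mixed models use all available data, account for non-independence of repeated measures and provide unbiased estimates if missing data are present". Section 8.3 defines the efficacy population as "Any participant who was randomized and provided baseline plus at least one other visit where the PANSS and PSS scales assessments were reassessed". Section 8.6 gives no dropout rate. It says that power remains sufficient (0.80) "even if a significant number of randomized participants fail to provide data for the proposed analyses".

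**The concern.** A likelihood-based mixed model handles dropout without bias when the chance of leaving depends only on data that were recorded. Section 5.3 ties leaving to the participant's current clinical state. If that state is not rated, the value that caused the exit is missing because of what it was. The model then predicts the rest of that participant's course from people with similar past scores who did not worsen, and the prediction is too favourable.

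This route off study is foreseeable. Section 4.3 requires a PANSS total of at least 70 and a positive-symptom exacerbation within the past year. Section 8.1 states unbiasedness without the missing-at-random condition, and no sensitivity analysis is planned. A participant who worsens and leaves before the first re-rating also drops out of the efficacy population altogether. An exit score that was not taken cannot be recovered later.

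**Working it through.** **1. The plan's own power figures.** Inputs from section 8.6: effect size 0.83, alpha 0.05, 33 per arm. For a two-sample t-test the noncentrality is d × √(n/2).
- n = 33: 0.83 × √16.5 = 3.37. Power is 0.913 two-tailed and 0.955 one-tailed (stated 0.90 and 0.95).
- n = 24: 0.83 × √12 = 2.88. Two-tailed power is 0.804 (stated 0.80).

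Every sample size in the table reproduces. The slack down to power 0.80 is 66 − 48 = 18 of 66 (27%) two-tailed, or 66 − 38 = 28 of 66 (42%) one-tailed. This allows for lost sample size. It says nothing about bias.

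**2. Gaps between ratings.** The table header puts V4 at week 2 and V6 at week 6, so the gap is about four weeks. The header puts V8 at week 10, but section 3.5 times the MCCB at weeks 6 and 12, which matches V6 and V8 in the MCCB row. The last gap is then about six weeks. These positions are uncertain, because the table conflicts with the text and may be damaged in extraction.

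**3. Size of the bias, main simulation.** All inputs except 0.83 are assumptions: 300,000 per arm, four post-baseline ratings, between-visit correlation 0.7 with decay, placebo change −0.30 SD, an effect growing to 0.83 SD, and withdrawal once a score worsens past a threshold. The fit is maximum likelihood for monotone missing data, which is equivalent to a mixed model with unstructured covariance, without the baseline covariate. Week-12 results in SD units, with the triggering score not recorded:

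| Withdrawn, placebo / WSE | Placebo, true → estimated | WSE, true → estimated | Difference, true → estimated |
|---|---|---|---|
| 4.7% / 2.3% | −0.300 → −0.347 | −1.127 → −1.148 | 0.827 → 0.801 |
| 13.0% / 7.1% | −0.302 → −0.421 | −1.130 → −1.190 | 0.829 → 0.769 |
| 21.6% / 12.6% | −0.298 → −0.490 | −1.131 → −1.234 | 0.833 → 0.743 |
| 28.7% / 17.7% | −0.300 → −0.553 | −1.129 → −1.268 | 0.829 → 0.715 |

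In the second row placebo shifts by 0.119 and WSE by 0.060, so the difference loses 0.119 − 0.060 = 0.059 (0.060 from the tabulated differences). About half of the placebo shift cancels. With the triggering score recorded, the estimated difference is within 0.001 of the truth in all four rows.

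**4. Equal withdrawal.** With no true effect and 28.8% leaving in each arm, both arms shift by about 0.26 SD and the difference moves only from −0.002 to −0.003. A separate run with 14% leaving in each arm also showed no bias. The case of more WSE withdrawals was not simulated; its direction follows by symmetry.

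**5. Early leavers.** In the four rows, 2.1%, 6.1%, 10.7% and 14.8% of placebo participants had no post-baseline PANSS and would fail section 8.3. With an exit rating none did.

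**6. Other assumed mechanisms.**
- Gradual worsening, adjacent correlation 0.85, 15-26% leaving, 33 per arm: 0.77-0.80 without an exit score and 0.83 with it. Power was 0.89-0.91 against 0.90-0.91.
- Weekly process, 1-26% of placebo and 0.1-10% of WSE leaving: 0.82 down to 0.68 without an exit score, and 0.83 to 0.85 with it assigned to the next PANSS visit.
- Stress case, abrupt worsening of 1.5 SD, correlation 0.7, 27% of placebo against 9% of WSE leaving: a true 0.87 is estimated as 0.59 without (power 0.61) and 0.82 with (power 0.81).

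**The case against.** The strongest reply is that a rating would often exist anyway. Sections 3.1 and 7.3 have symptoms rated at each visit, 7.3 uses the scales for safety monitoring as well, section 3.2 lets participants come in early if needed, and section 10.1 promises every effort to obtain complete data. A worsening participant seen at V5, V7 or an extra visit might well be rated. This stands as a limit: not specified is not the same as not taken. It does not close the gap. The schedule contradicts the every-visit wording, and none of these passages requires a rating at withdrawal. The final procedures in section 7.12 concern a study-wide safety stop, with laboratory tests as the example.

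The route can also be questioned. Worsening, intolerance and withdrawn consent are not among the numbered grounds of 11.3, so applying its termination steps to them is an inference, though no other steps are given. An exit rating cannot be obtained from someone lost to follow-up and may be refused by someone withdrawing consent.

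On size, worsening need not end participation: psychotropic changes are recorded and coded (sections 3.6, 7.3 and 8.2), and 5.3 withdraws only when worsening prevents continuation. In the gradual scenario of step 6 power hardly changed. If placebo loses more, the error works against WSE. All of this stands and keeps the likely effect modest.

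**Conclusion.** The gap is real: no passage requires a PANSS at early withdrawal, and the plan followed as written can lose the score that led to it. Under assumed gradual worsening with more placebo withdrawals, a true 0.83 SD is estimated at about 0.68-0.82. For scale, true effects of 0.75, 0.70 and 0.65 would have two-tailed power of 0.85, 0.80 and 0.74 at a full 33 per arm. The withdrawal rates, correlations and thresholds are all assumptions, because the documents give no dropout rate.

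A reader might infer three stronger things, which the documents do not support.
- That worsening never reaches the primary outcome: worsening rated at a visit before withdrawal does enter the model.
- That only placebo is flattered, so the effect must be understated: both arms shift, and the direction depends on which arm loses more to worsening.
- That the effect could be expected to fall to 0.59: that figure is a stress case, and nothing in the plan supports 27% of placebo leaving for worsening. The 18 of 66 is slack for loss from any cause, not a forecast.

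This should be corrected, with medium confidence in its size.

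**What to change.** - **Section 11.3:** add to the termination procedures a PANSS, CGI and PSS by the blinded rater at withdrawal, where the participant agrees and can be reached. Apply it to every route off study and name section 5.3.
- **Section 3.4:** mark the last PANSS/CGI/PSS column as V8 or early termination. Reconcile this row with sections 3.1 and 7.3 on which visits carry the scales.
- **Section 8.1:** assign the exit rating to the scheduled PANSS visit whose window contains it, otherwise to the next one. Add a sensitivity analysis of this assignment: 5.3 has such participants stabilised afterwards, so an acute score may not represent week 12. A check with persistent worsening showed an overshoot of only about 0.01 SD, and the weekly simulation at most 0.85 against 0.83. Transient worsening was not examined. State the missing-at-random condition beside the unbiasedness claim.

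The cost is one PANSS interview, 20-30 minutes by section 3.5, plus the CGI and PSS, usually at a contact that already takes place and with existing raters. No dose, withdrawal criterion or care changes. Some exits will be refused, by telephone or lost, so the loss is reduced, not removed.
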